
	(Cp) of $\geq 30\%$ for the primary efficacy endpoint. Of note, a standardized effect size of 0.49 would not meet criteria to continue. There will be no stopping for early efficacy.
Objectives/ Endpoints	
The primary objective of the proposed research study is to assess postoperative analgesia that extends beyond the duration of the local anesthetic interventions to prepare for a subsequent pivotal definitive clinical trial with the RELAY device compared to sham control.
 
Primary endpoint: Difference in the average daily pain intensity for Days 1-7 as measured with the Numeric Rating Scale (NRS) within the Brief Pain Inventory (BPI) via the RELAY device compared to sham control.
 
• Hypothesis 1: Neuromodulation with the RELAY device will decrease average pain intensity for Days 1-7 following foot and shoulder surgery currently treated with a single-injection peripheral nerve block (as measured with the NRS within the BPI). 
The key secondary objectives are:
 
1) To estimate the effect on opioid consumption of neuromodulation via the RELAY device as compared to sham control 
Key secondary endpoint 1 (hierarchical: tested for significance only if the primary endpoint achieves significance at alpha 1-sided <0.025): Difference in the cumulative opioid use (oxycodone equivalents) for Days 1-7 via the RELAY device compared to sham control.
 
• Hypothesis 2: Neuromodulation with the RELAY device will decrease opioid consumption within the week following foot and shoulder surgery currently treated with a single-injection peripheral nerve block (measured in oxycodone equivalents), as measured both with daily and cumulative opioid consumption within the first postoperative week). 
2) To estimate the effect on physical and emotional functioning of neuromodulation via the RELAY device as compared to sham control 
Key secondary endpoint 2 (hierarchical: tested for significance only if the primary endpoint and key secondary endpoint 1 both achieve significance at alpha 1-sided <0.025): Difference in BPI interference subscale on Day 3 as measured with the NRS within the BPI Inventory via the RELAY device compared to sham control.
 
• Hypothesis 3: Neuromodulation with the RELAY device will decrease pain's interference in physical and emotional functioning within the week following foot and shoulder surgery currently treated with a single-injection peripheral nerve block (as measured with the Interference Subscale of the BPI). 
Other Secondary Endpoints to include:
 
• Interference in physical and emotional functioning (as measured with the Interference Subscale of the BPI) on Post-op Day 7• Opioid use (oxycodone equivalents) on Post-op Days 1, 2, 3, 4, 7, 8 and 14• Awakenings due to pain on Post-op Days 1, 2, 3, 4, 7, 8 and 14

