3 OBJECTIVES AND ENDPOINTS

OBJECTIVES	ENDPOINTS	JUSTIFICATION FOR ENDPOINTS
Primary		
To assess postoperative analgesia that extends beyond the duration of the local anesthetic interventions to prepare for a subsequent pivotal definitive clinical trial with the RELAY device as compared to sham control.	Difference in the average daily pain intensity for Days 1-7 as measured with the NRS within the BPI between the RELAY device and sham control arms.	Pain negatively influences physical and emotional functioning.
Key Secondary		
To estimate the effect on opioid consumption of neuromodulation via the RELAY device as compared to sham control	Neuromodulation with the RELAY device will decrease cumulative opioid consumption during the first postoperative week following foot and shoulder surgery currently treated with a single-injection peripheral nerve block (measured in oxycodone equivalents).	Opioid use has negative individual and society consequences
To estimate the effect on physical and emotional functioning of neuromodulation via the RELAY device as compared to sham control	The physical and emotional functioning of participants will be improved on postoperative Day 3 following foot and shoulder surgery currently treated with a single-injection peripheral nerve block (as measured with the BPI Interference Subscale)	Pain negatively influences physical and emotional functioning.
Other Secondary		
To estimate the effect on physical and emotional functioning of neuromodulation via the RELAY device as compared to sham control	The physical and emotional functioning of participants will be improved on postoperative Day 7 following foot and shoulder surgery currently treated with a single-injection peripheral nerve block (as measured with the BPI Interference Subscale)	Pain negatively influences physical and emotional functioning.
To estimate the analgesic effect of neuromodulation via the RELAY device as compared to sham/placebo for the RELAY device following foot and shoulder surgical procedures at various time points post-treatment	Neuromodulation with the RELAY device will decrease pain intensity (as measured by the “average” and “worst” (maximum) daily NRS within the BPI) on Days 1, 2, 3, 4, 7, 8, and 14 following foot and shoulder surgery currently treated with a single-injection peripheral nerve block.	Pain negatively influences physical and emotional functioning.

OBJECTIVES	ENDPOINTS	JUSTIFICATION FOR ENDPOINTS

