To estimate the analgesic effect of neuromodulation via the RELAY device as compared to sham/placebo for the RELAY device following foot and shoulder surgical procedures at various time points post-treatment	Neuromodulation with the RELAY device will decrease pain intensity (as measured by “current” and “least” daily NRS within the BPI) on Days 3 and 7 following foot and shoulder surgery currently treated with a single-injection peripheral nerve block.	Pain negatively influences physical and emotional functioning.
To estimate the effect on opioid consumption of neuromodulation via the RELAY device as compared to sham/placebo for the RELAY device following foot and shoulder surgical procedures at various time points post-treatment	Neuromodulation with the RELAY device will decrease daily opioid consumption following foot and shoulder surgery currently treated with a single-injection peripheral nerve block (measured in oxycodone equivalents on Days 1, 2, 3, 4, 7, 8 and 14).	Opioid use has negative individual and society consequences
To estimate the effect on sleep disturbances of neuromodulation via the RELAY device as compared to sham/placebo for the RELAY device following foot and shoulder surgical procedures at various time points post-treatment	Neuromodulation with the RELAY device will decrease cumulative awakenings due to pain following foot and shoulder surgery currently treated with a single-injection peripheral nerve block (evenings of postoperative Days 1, 2, 3, 4, 7, 8 and 14)	Poor sleep quality is correlated with inferior analgesia and functioning
To evaluate the masking quality of the study protocol	The masking assessment on Post-op Day 1	Successful masking reduces bias

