8 STUDY ASSESSMENTS AND PROCEDURES

8.1 EFFICACY ASSESSMENTS

Outcome measurements. We have selected outcome measures that have established reliability and validity, with minimal inter-rater discordance, and are recommended for pain clinical trials by the Initiative on Methods, Measurement, and Pain Assessment in Clinical Trials (IMMPACT) consensus statement. The primary outcome measure will be the median “average” daily **pain intensity** for Days 1-7 as measured with the NRS within the BPI. The primary analysis will compare the two treatments (inter-subject comparisons) in which half of the participants will receive active neuromodulation and the other half a sham/placebo neuromodulation. Endpoints will be evaluated on postoperative Days 1, 2, 3, 4, 7, 8, and 14. In addition, participants will receive a phone call the evening of postoperative Day 0 (the day of surgery) to answer any questions they may have about the stimulator or study protocol.

Each time the questionnaire is applied, participants will be instructed to respond for the previous 24 hours. The exception will be on Day 1 because at these time points, the interest is in participants’ experiences subsequent to discharge from the recovery room. During this day only, participants will be instructed to respond for the period of time since they were discharged from the recovery room.

We will record basic anthropomorphic characteristics (e.g., age, physiological sex, height, and weight), intervention characteristics (e.g., pulse generator parameters, catheter insertion duration, minimum/maximum comfortable amplitude), surgical characteristics (e.g., surgical duration) and protocol deviations / adverse events.

All data collection following the day of the intervention (Day 0) will be collected by telephone from the University of California San Diego by the investigators, Program Manager, and/or research coordinators specifically trained in these instruments’ application, minimizing inter-rater discordance and standardizing responses across all enrolling centers. Observers masked to treatment group assignment will perform all postoperative assessments. Each data collection phone call will require approximately 5 minutes.

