In addition to the outcomes described below, we will record awakenings due to pain at each data collection phone call, as well as any sensory deficits for participants with continuous peripheral nerve blocks, and patient-controlled changes to the neuromodulation amplitude. On postoperative day 1 we will query participants on whether they believe they are receiving active or sham stimulation (a masking assessment).

Hypothesis 1: Neuromodulation with the RELAY device will decrease **pain intensity** for Days 1-7 following foot and shoulder surgery currently treated with a single-injection peripheral nerve block (as measured with the NRS within the BPI).

Current/present, worst, least, and average ‘surgical pain will be assessed using the NRS as part of the BPI (short form), with the “average” pain scores collected on postoperative days 1, 2, 3, 4 and 7 designated as the primary endpoint. The NRS is a highly-sensitive measure of pain intensity with numbers ranging from 0 to 10, zero equivalent to no pain and 10 equivalent to the worst imaginable pain. The NRS has been demonstrated to be a valid and reliable measure in multiple pain states and following analgesic interventions. In addition, NRS scores correlate well with other measures of pain intensity, and demonstrate high test-retest reliability in chronic nociceptive and neuropathic pain states. These NRS characteristics led to recent IMMPACT consensus recommendations for use of the 10-point NRS of pain intensity for pain trials.

Hypothesis 2: Neuromodulation with the RELAY device will decrease **opioid consumption** within the week following foot and shoulder surgery currently treated with a single-injection peripheral nerve block (measured in oxycodone equivalents), as measured both with daily and cumulative opioid consumption within the first postoperative week).

Opioid analgesic consumption will be recorded at all time points (Table 2), with the secondary outcome measure of greatest importance being the cumulative opioid dose in oral oxycodone equivalents for the first 7 postoperative days following recovery room discharge. The two treatment groups' daily opioid consumption will also be compared at all timepoints, including Day 14.

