9.4.2 ANALYSIS OF THE PRIMARY EFFICACY ENDPOINT(S)

The primary analytic approach will be an unadjusted two-sample Mann-Whitney U test of the median value of each participant's average daily NRS for Days 1, 2, 3, 4, and 7 (data is not collected on Days 5 and 6). If any key variables are imbalanced at baseline, a linear regression model, or appropriate generalized linear model, adjusting for those variables will be applied. The p-value and 95% confidence interval associated with the estimated group difference in average daily NRS will be provided. $P<0.05$ will be considered statistically significant for the primary outcomes.

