9.4.3 ANALYSIS OF THE SECONDARY ENDPOINT(S)

Continuous endpoints will be analyzed with the same approach as the primary endpoint. Binary endpoints will be analyzed with Fisher's Exact test for two proportions, or logistic regression in the event of imbalance on key baseline variables. Ordinal endpoints will be analyzed with the Armitage trend test, or cumulative link regression model as warranted. We will test key secondary outcomes using a serial gatekeeping procedure. Nominal 95% confidence intervals will be provided for secondary analyses.

Study-wide Type I error control. We will use a serial gatekeeping procedure to control the study-wide type I error at 0.05 [Mascha EJ, Turan A: Joint hypothesis testing and gatekeeping procedures for studies with multiple endpoints. *Anesth Analg* 2012; 114: 1304-17]. For this procedure we therefore have prioritized (*a priori*) the study outcomes (**Table below**). Analysis will proceed in that order, and testing will proceed through each "gate" to the next set if and only if the outcome in the current set reaches significance. The significance level for each set will be 0.05 times a cumulative penalty for non-significant results in previous sets (i.e., a "rejection gain factor" equal to the cumulative product of the proportion of significant tests across the preceding sets). We will use the corresponding 2-tailed alpha level of 0.05 for the gatekeeping, as all sets involve 2-tailed tests. Treatment effects will also be assessed at individual time points regardless of preceding gatekeeping results, and no other adjustments will be made for testing multiplicity.

Serial gatekeeping procedure

Sets	Time frame	Required to pass to next set
------	------------	------------------------------

1: Pain intensity (median of 5 daily “average” NRS)	1 st week	Significance on this outcome
2: Cumulative opioid use (oxycodone equivalents)	1 st week	Significance on this outcome
3: BPI interference subscale	Postop Day 3	Significance on this outcome
4: Pain intensity (median of 5 daily “worst” NRS)	1 st week	Significance on this outcome
5: BPI interference subscale	Postop Day 7	Significance on this outcome
6: Cumulative awakenings due to pain	1 st week	Significance on this outcome
7: Pain intensity (“average” NRS)	Postop Day 7	Significance on this outcome
8: Pain intensity (“worst” NRS)	Postop Day 7	Significance on this outcome
9: Opioid use (oxycodone equivalents)	Postop Day 7	Significance on this outcome

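### The seven-day opioid total cannot be computed as defined, because the plan gives no source for opioid use on Days 5 and 6

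*Combined protocol and SAP*

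**What the plan says.** The endpoint is described as covering a full week wherever it appears:

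- Synopsis (1.1): "Difference in the cumulative opioid use (oxycodone equivalents) for Days 1-7 via the RELAY device compared to sham control".
- Section 3: the device will "decrease cumulative opioid consumption during the first postoperative week following foot and shoulder surgery".
- Section 8.1, which ranks it first among the secondary outcomes: "cumulative opioid dose in oral oxycodone equivalents for the first 7 postoperative days following recovery room discharge".
- Section 9.4.3, set 2 of the serial testing table: "Cumulative opioid use (oxycodone equivalents"), with the first week as its time frame.

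Collection is narrower. Section 8.1 records opioid use at all time points. Section 3 lists these for daily consumption: "measured in oxycodone equivalents on Days 1, 2, 3, 4, 7, 8 and 14". The schedule tables in 1.1 and 1.3 have no column for Day 5 or Day 6.

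On recall, section 8.1 says: "Each time the questionnaire is applied, participants will be instructed to respond for the previous 24 hours". The one exception is the Day 1 call: "During this day only, participants will be instructed to respond for the period of time since they were discharged from the recovery room".

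Section 9.4.2 acknowledges, for the pain score, that "data is not collected on Days 5 and 6", and defines the primary endpoint as a median of the five available daily values. Section 9.4.1 provides multiple imputation by chained equations for missing data that were not expected.

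**The concern.** A median of five daily scores is still a median when two days are skipped. A total is not: it needs every day, or a rule for the days that were not asked about. The pain endpoints were adapted to the call schedule and the opioid total was not.

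This endpoint matters for two reasons. It is second in the testing order, so its result decides whether any later endpoint is formally tested. And section 2.2 reports that the earlier RELAY pilot missed its expected pain efficacy but saw roughly a 50% reduction in opioid use, so the weekly opioid difference is a figure the planned larger trial may well rely on. The device is still in place on Days 5 and 6, because removal comes after 7 days (1.1, 6.1.1). An effect on those days would go unmeasured, and the data cannot be reliably recovered later.

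**Working it through.** **1. Coverage.** From recovery-room discharge to the Day 7 call there are seven daily windows. The calls on Days 1, 2, 3, 4 and 7 cover five of them: 5/7 = 71.4%. The Day 4 and Day 7 calls are 72 hours apart and the Day 7 call reaches back 24, so 48 hours are uncovered: 2/7 = 28.6% of the week. The Day 8 call, at 24 hours, does not help.

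**2. Could imputation fill it?** No. The gap is planned, whereas section 9.4.1 addresses unexpected gaps. With no Day 5 or Day 6 value in any participant, there are no observed values to which an imputation model for those days could be fitted.

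**3. Share of the total unobserved.** The documents give no daily opioid profile, so I assume that use changes by a constant ratio r per day. Share on Days 5-6 = (r⁴ + r⁵) / (r⁰ + … + r⁶).

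| Daily fall (assumed) | r | Share unobserved |
|---|---|---|
| none | 1.0 | 28.6% |
| 10% | 0.9 | 23.9% |
| 20% | 0.8 | 18.7% |
| 30% | 0.7 | 13.3% |
| 40% | 0.6 | 8.5% |

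**4. The answer depends on an unstated rule.** Estimated total as a percentage of the true seven-day total, for four assumed profiles (Days 1 to 7):

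| Profile | Five-day sum | × 7/5 | Day 4 carried forward | Day 7 carried back | Linear interpolation |
|---|---|---|---|---|---|
| Flat | 71% | 100% | 100% | 100% | 100% |
| Linear fall, 7 to 1 | 82% | 115% | 111% | 89% | 100% |
| Halving every 2 days | 86% | 121% | 109% | 94% | 102% |
| 1, 4, 5, 4, 3, 2, 1 | 75% | 105% | 115% | 85% | 100% |

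Interpolation does well here because these profiles are smooth after Day 4. The plan specifies none of these rules.

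**5. Effect in milligrams.** With a constant daily effect, a five-day sum shows 5/7 = 71% of the weekly difference. If there is no effect on Day 1, it shows 4/6 = 67%. If instead the effect is proportional to use that falls 10% to 40% a day, the sum keeps 1 − 0.239 = 76% to 1 − 0.085 = 91.5%. With no Day 1 effect as well, the denominator becomes r¹ + … + r⁶ and the sum keeps about 70% to 86%.

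**6. Sensitivity.** Assume equal daily variance and within-person correlation ρ. The standardized effect of the five-day sum relative to the seven-day sum is (5/7) × √[(7 + 42ρ)/(5 + 20ρ)]. With no Day 1 effect, 4/6 replaces 5/7.

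| ρ | Constant effect | No Day 1 effect |
|---|---|---|
| 0.3 | 0.953 | 0.890 |
| 0.5 | 0.976 | 0.911 |
| 0.7 | 0.989 | 0.923 |

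**7. Power, as an illustration.** The plan states no power for this endpoint. Its only power figure, 85.2% for pain (section 9.2: 20 per group, SD 2.05, difference 2), is reproduced by a two-sided 0.05 t-test (85.23%), so I use the same method. If the seven-day sum had an effect size of 0.8 (assumed), power with 20 per arm is 69%. With a constant effect the effect size falls to 0.8 × 0.953 = 0.76 up to 0.8 × 0.989 = 0.79, and power to 65-68%. With no Day 1 effect it falls to 0.71-0.74, and power to 59-62%. The plan's test is Mann-Whitney, so these are approximations.

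**The case against.** The best reply is that the documents do not forbid a longer recall for opioids. The 24-hour instruction speaks of the questionnaire and does not name the opioid item. Section 8.1 introduces opioid use separately and cites a Table 2 that does not appear under that number in the text. The case report form may already ask for use since the last call. That is possible, and it would close the gap in practice. But the plan would then state no recall period for opioids at all, and section 8.1 would still need the same sentence. Since-last-contact wording does exist in section 8.2, but only for adverse events.

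A second reply is that the plan uses Days 1-7 and first week as labels for the five collected days, as it does for the primary endpoint, so the opioid total is simply the sum over those days. This has some support in section 9.4.3, but it conflicts with the literal reference to the first 7 postoperative days in section 8.1.

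A third reply is that the harm is conditional and modest. This largely stands. Understatement follows only if a five-day sum is reported as the weekly total. The 71% and 67% figures are the unfavourable end of the milligram range, and the statement about Days 5 and 6 in section 9.4.2 comes from the pain analysis, so it shows that no data are collected on those days, not what the Day 7 call asks.

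**Conclusion.** The concern holds. Read as written, the plan observes five of the seven days that its first key secondary endpoint claims to total, and gives no rule for the other two. Depending on the course of opioid use, 8.5% to 28.6% of the total is missing. A five-day sum would show 71% of the weekly milligram difference under a constant daily effect, 67% with no Day 1 effect, and more than that if the effect shrinks as use falls. The standardized effect keeps 95-99%, or 89-92% with no Day 1 effect.

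The daily profiles, correlations (0.3 to 0.7) and the 0.8 effect size are assumptions; the count of days is not. Type I error is not inflated by the gap itself, since both arms are affected alike, and the primary endpoint is unaffected. What needs correcting is an estimate that is understated or depends on a rule chosen later, at the second step of the testing sequence.

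**What to change.** Keep the call schedule. At the existing Day 7 call, ask for opioid taken on Days 5, 6 and 7 separately, covering the time since the Day 4 call. State this in section 8.1 as a second exception to the 24-hour recall, and define the endpoint as the sum of seven daily values. If the case report form already asks for use since the last call, write that into section 8.1.

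The alternative is to redefine the endpoint in sections 1.1, 3, 8.1 and 9.4.3 as the sum over Days 1-4 and 7, and to label it as such in every report. That makes the definition computable but still leaves any effect on Days 5 and 6 unmeasured. Either choice should be fixed before unmasking.

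The first option costs one or two extra questions in a five-minute call and one sentence of protocol text. Its drawback is recall of up to three days for Days 5 and 6, so those values will be less precise than the 24-hour ones.

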8.2 SAFETY AND OTHER ASSESSMENTS

Prospective participants will be provided with informed consent and then screened for inclusion and exclusion criteria. The following safety and eligibility procedures will occur during that time:

- **Study Eligibility** – A study investigator will review all medical history, medications and the inclusion/exclusion criteria with the participants.
- **Informed Consent** - Participants will provide written informed consent prior to any other study procedures.
- **Vital Signs** – These include blood pressure, heart rate, temperature and respiratory rate as well as pulse oximetry and continuous 5-lead ECG.
- **Adverse Event Collection** – Participants' progress notes will be followed during days of hospitalization and any adverse events recorded. Following discharge, investigators will inquire about any adverse or unexpected events that have occurred since the previous contact. All events will be evaluated by a study investigator and will be followed until resolution.

Any of the safety assessment results will be made available to participants should they request them.

